3.3.6 Interim Analysis

For the Data Safety and Monitoring Board (DSMB), interim analyses will be performed by the DCC. There will be 3 looks at the data; the first when 79 participants are enrolled (which was shown to the DSMB on August 30, 2007) among whom 42 participants were enrolled on or before July 1, 2006, i.e., at least 1 year ago, the second when 92 participants reach the 1 year follow-up and the last when all 184 participants reach the 1 year follow-up.

With this revised plan, the power remains at 85%. The new O'Brien-Fleming boundaries will be:

NAC Study Protocol

-4.550, 4.550 corresponding to a nominal α of 0.00005 at the first look
-2.963, 2.963 corresponding to a nominal α of 0.00305 at the second look
-1.969, 1.969 corresponding to a nominal α of 0.04900 at the third look

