3.3 Data Collection and Statistical Considerations

3.3.1 Sample Size Calculation:

It is anticipated that 90 children with PALF will be admitted to the clinical centers each year. Of those, approximately 20% will likely be due to acetaminophen overdose leaving 72 patients eligible for the study. We anticipate 25% of the eligible patients will not be enrolled, leaving an estimated 54 patients per year to be randomized. The one year death rate without transplant of 15% is lower than in the adult population. However, while a greater percentage of children receive a liver transplantation (40%), 40% of these children die, leaving an estimated overall survival with or without a liver transplant of 69% in the placebo arm. See diagram provided in Appendix 1 on page 20.

Based on these data, the estimated sample size to evaluate the efficacy of IV-NAC in the treatment of ALF in children was calculated. The original sample size was calculated assuming a one year survival rate for the patients in the treatment arm is 86.5% and 6 planned interim analyses. This comparison would need 92 patients in each arm (184 total) to achieve 80% power (likelihood of rejecting the hypothesis of equal survival rates) with a two-sided test of survival (log-rank test) at $\alpha=0.054$. The external Data and Safety Monitoring Board has accepted a revised interim monitoring plan for efficacy consisting of a single interim analysis when half of the sample of 184 reaches the one-year follow-up. Keeping the sample size at 184, this effectively lowers the type I error to 0.05 while maintaining 80% power.

Due to preliminary findings in a similar study, an additional interim analysis was performed. There will be 3 looks at the data; the first when 79 participants are enrolled (which was shown to the DSMB on August 30, 2007) among whom 42 participants were enrolled on or before July 1, 2006, i.e., enrolled for at least 1 year, the second when 92 participants reach the 1 year follow-up and the last when all 184 participants reach the 1 year follow-up.

With this revised plan, the power remains at 85%. The new O'Brien-Fleming boundaries will be:

- 4.550, 4.550 corresponding to a nominal α of 0.00005 at the first look
- 2.963, 2.963 corresponding to a nominal α of 0.00305 at the second look
- 1.969, 1.969 corresponding to a nominal α of 0.04900 at the third look

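### The first-look nominal alpha of 0.00005 does not belong to the boundary of 4.550; the two-sided value is 0.0000054, about nine times smaller

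*Protocol*

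**What the plan says.** Section 3.3.6 (Interim Analysis) sets three looks: the first with 79 participants enrolled, "among whom 42 participants were enrolled on or before July 1, 2006"; the second when 92 reach one year; the last when all 184 do. The first was shown to the DSMB on August 30, 2007. The list introduced by "The new O'Brien-Fleming boundaries will be" pairs each z-boundary, given with both signs, with a nominal alpha. Its first row reads "4.550 corresponding to a nominal α of 0.00005 at the first look". The second row pairs 2.963 with 0.00305, and the third pairs 1.969 with 0.04900.

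The same three pairs stand in section 3.3.1 (Sample Size Calculation). That section describes the design as one "with a two-sided test of survival (log-rank test") and says of the earlier single-interim plan that "this effectively lowers the type I error to 0.05 while maintaining 80% power".

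**The concern.** Each row presents a z-boundary and a nominal alpha as two expressions of one threshold. In the first row they are not equivalent: a z of 4.550 lies much further into the tail than an alpha of 0.00005 implies. Someone comparing the log-rank z with 4.550 and someone comparing its p-value with 0.00005 would apply different efficacy rules at that look.

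The row also records how much alpha the first look used. Section 3.3.1 says that this look was added because of preliminary findings in a similar study. An added look is where a later reader is most likely to check the alpha accounting. Both sections that define the rule carry the same figure, so neither corrects the other.

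**Working it through.** **Inputs.** Boundaries 4.550, 2.963 and 1.969 with stated alphas 0.00005, 0.00305 and 0.04900 (sections 3.3.1 and 3.3.6). Two-sided log-rank test with overall type I error 0.05 (section 3.3.1). Information fractions 42/184 = 0.228, 92/184 = 0.5 and 184/184 = 1, taking participants with one year since enrolment as the measure of information (section 3.3.6).

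**Step 1. Convert each boundary to its two-sided alpha,** 2 × (1 − Φ(z)).

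| Look | Boundary | Alpha stated | Alpha computed | Stated / computed |
|---|---|---|---|---|
| 1 | 4.550 | 0.00005 | 0.00000536 | 9.3 |
| 2 | 2.963 | 0.00305 | 0.003047 | 1.00 |
| 3 | 1.969 | 0.04900 | 0.04895 | 1.00 |

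Rows 2 and 3 reproduce. In row 3 the small difference is rounding of the boundary: an alpha of 0.04900 gives z = 1.9686, which rounds to 1.969. Row 1 does not reproduce.

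**Step 2. Convert the stated alpha back to z.** Two-sided, Φ⁻¹(1 − 0.00005/2) = 4.056, not 4.550.

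**Step 3. Look for a reading that rescues row 1.**

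- One-sided alpha: 1 − Φ(4.550) = 0.0000027, which is further from 0.00005. A one-sided 0.00005 gives z = 3.891.
- Rounding of the boundary: z from 4.5495 to 4.5505 gives 0.00000538 to 0.00000535.
- Rounding of the alpha: 0.00000536 at five decimals is 0.00001, not 0.00005.
- Cumulative alpha spent: at the first look this equals the nominal alpha, so it is the same number.

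**Step 4. Decide which of the two figures is wrong.** The Lan-DeMets O'Brien-Fleming-type spending function for two-sided 0.05 is α(t) = 4 × [1 − Φ(2.2414/√t)], where 2.2414 = Φ⁻¹(1 − 0.05/4).

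- At t = 42/184 it spends 0.0000054, giving z = 4.548. With t rounded to 0.228, z = 4.550.
- Carried on by numerical integration to t = 0.5 and t = 1, it gives z = 2.963 and 1.969, with nominal alphas 0.00305 and 0.04900.

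All three printed boundaries and two of the three printed alphas come out of this one calculation. Only the 0.00005 does not.

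**Step 5. Effect on overall type I error.** With later boundaries of 2.963 and 1.969, the overall two-sided error is 0.04995 if the first boundary is 4.550 and 0.04997 if it is 4.056, a difference of 0.00002.

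**The case against.** The strongest reply accepts the arithmetic and disputes the consequence.

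- *The boundary is the rule and the alpha only annotates it.* The list is introduced as boundaries, and a statistician can tell from the protocol which figure governs. This is fair, and it is why the correction is to the alpha alone. It does not make the annotation harmless, because a stated nominal alpha can be used directly as a p-value threshold.
- *The disputed band was hardly reachable.* This largely stands. Take the 42 participants as 21 per arm, with no censoring, no tied death times and every death in one arm. The log-rank |z| is then 3.85 with 11 deaths to 0, 4.10 with 12, 4.36 with 13 and 4.62 with 14. Only 12 or 13 deaths to 0 falls between 4.056 and 4.550. The survival rates in section 6.2 imply about 21 × 0.31 = 6.5 placebo deaths and 21 × 0.135 = 2.8 NAC deaths.
- *The look is past and the trial went on.* True. Correcting the figure changes no future decision.
- *The protocol does not show which figure the DSMB used.* Also true. That part is a query to be settled from the DSMB record, not an established fault.

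These points limit the importance of the error. None makes the printed figure right.

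**Conclusion.** The first-look nominal alpha is wrong as printed in both sections. It is 0.00005 where the boundary of 4.550 gives 0.0000054, a factor of 9.3. The boundary itself is consistent with the design. The arithmetic mismatch rests only on the normal distribution and the two-sided test. The conclusion that the alpha, not the boundary, is in error rests in addition on O'Brien-Fleming-type spending at 42/184, which reproduces every other figure in the table.

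The consequence is confined to the first look: only a |z| between 4.056 and 4.550 would have been judged differently. Overall type I error moves by about 0.00002, and the second and third boundaries need no change. It should be corrected because it is a threshold in the efficacy stopping rule, but it does not threaten the validity of the trial.

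**What to change.** In sections 3.3.1 and 3.3.6, replace the first-look nominal alpha of 0.00005 with 0.0000054 (two-sided), and leave the boundary of 4.550 as it is. Two significant figures are preferable to 0.000005, because 0.000005 converts back to z = 4.565, whereas 0.0000054 gives 4.549. State once that the nominal alphas are two-sided.

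Separately, confirm from the DSMB record that the August 30, 2007 analysis was judged against |z| = 4.550, and note this in the file. The cost is one figure changed in two places and one look at existing records; no boundary, sample size or later analysis is affected.

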4.5 Risk/Benefit Ratio

A possible risk is a breach of confidentiality, although steps have been taken to minimize such an occurrence. All information collected for this research study will be kept confidential. Patients' names will be used only for the informed consent form and medical chart reviews. Patients will be given unique study identifiers, which will be written on all data collection forms and biospecimens. In addition, data collection forms will be kept in secured, locked files. Known breaches of confidentiality will be reported to NIDDK.

The main adverse event reported in previous studies of NAC was a rare hypersensitivity reaction, manifested by rash or wheezing, and occurring with increased frequency in patients with a previous asthmatic diathesis. In each instance, use of intravenous anti-histamine (diphenhydramine) or corticosteroids aborted the attack and no instances of severe reactions have been reported. In most instances, the infusions were not discontinued and all symptoms resolved once diphenhydramine was instituted and the rate of infusion slowed.

Unusual events and anaphylactic reactions that occur during the seven day treatment period will be reported on a separate adverse event reporting sheet, and faxed to the Data Coordinating Center within 24 hours of knowledge of event. All Serious Adverse Event (SAE) reports received by the Data Coordinating Center will be forwarded to the Medical Safety Officer, the Data Safety and Monitoring Board (DSMB), the NIDDK project officer, and the IND holder. Serious adverse events that occur during the course of the trial and that meet criteria for expedited reporting will be forwarded to the FDA within 24 hours of receipt.

A DSMB, with members appointed by the NIDDK, consists of individuals who are independent of the institutions and investigators participating in the PALF study and who have no financial ties to the outcome of the trial. The ongoing review of the data by this independent committee assures the investigators and the NIDDK that the trial can continue without jeopardizing patient safety. The DSMB charter was developed by the NIDDK. The data and safety monitoring plan was approved by the DSMB. The roster and charter of the DSMB members will be provided to investigators participating in the study for submission to their IRB.

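### The protocol's only numerical stopping limits are symmetric, so excess deaths on NAC must meet the same strict standard as a claim of benefit: about 1.8 to 2.1 times the placebo deaths at the second look

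*Protocol*

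**What the plan says.** The primary endpoint is overall survival at one year, with or without transplant (3.3.2), compared by a log-rank test (3.3.5), two-sided in the sample size section (3.3.1). Sections 3.3.1 and 3.3.6 print the same three pairs of limits:

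- first look: "4.550, 4.550 corresponding to a nominal α of 0.00005 at the first look";
- second look: "2.963, 2.963 corresponding to a nominal α of 0.00305 at the second look";
- third look: "1.969, 1.969 corresponding to a nominal α of 0.04900 at the third look".

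In 3.3.6 each pair is a negative and a positive value of equal size. The first look took place with 79 children enrolled, "among whom 42 participants were enrolled on or before July 1, 2006". The next is timed as "the second when 92 participants reach the 1 year follow-up". The last comes when all 184 have done so.

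Section 3.3.1 describes the plan that came just before this one as a "revised interim monitoring plan for efficacy consisting of a single interim analysis when half of the sample of 184 reaches the one-year follow-up". The current plan adds a look to it.

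Section 4.5 sets up a DSMB that receives quarterly adverse-event summaries and serious adverse event reports, meets twice a year, reviews safety and efficacy in closed session, and may recommend early termination. It gives no numerical threshold for excess deaths. It refers to a DSMB charter and an approved data and safety monitoring plan; neither is shown. Appendix 6.2 mentions boundaries for both hypotheses, but for the superseded six-look plan and without values.

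**The concern.** A strict early limit on the benefit side protects the type I error of a claim that NAC works. That reason does not carry over to the harm side: nobody needs proof at the 0.3% level that an unapproved use of a drug raises mortality in children before discussing whether to continue. By mirroring the benefit limit, the protocol sets the same bar for both.

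Safety is part of the primary objective. Appendix 6.6 concedes that added toxicity will be hard to recognise against multi-organ failure, so the comparison of deaths is the most informative harm signal available. At stake is whether the one printed number that the DSMB can hold against that signal would flag a large excess of deaths at the second look.

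**Working it through.** **Inputs.** Limits ±4.550, ±2.963, ±1.969 (3.3.6). Looks at 42, 92 and 184 children with one year of follow-up, so information fractions 42/184 = 0.228, 0.5 and 1. Placebo mortality 31%, from "leaving an estimated overall survival with or without a liver transplant of 69% in the placebo arm" (3.3.1). Equal arms.

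**Reproducing the plan's limits.** Lan-DeMets O'Brien-Fleming spending with 0.025 in each tail at these fractions gives 4.548, 2.963 and 1.969. The nominal two-sided levels at the last two looks are 0.00305 and 0.0490, as printed. The limits are correctly derived symmetric limits. (The nominal level printed at the first look does not match its limit: 4.550 corresponds to 0.0000054. That is a separate matter.)

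**Second look, one-year completers, 46 per arm.** 31% of 46 is about 14 placebo deaths. With n per arm and pooled proportion p,

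z = (NAC proportion − placebo proportion) / √[p(1 − p) × 2/n].

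- 14 v 28: p = 42/92 = 0.4565; z = 0.3043 / √(0.4565 × 0.5435 × 2/46) = 0.3043/0.1039 = 2.93, not crossed.
- 14 v 29: p = 43/92 = 0.4674; z = 0.3261/0.1040 = 3.13, crossed.

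A log-rank approximation with proportional hazards crosses at 14 v 28 (z = 2.98). The ratio is 28/14 = 2.0 to 29/14 = 2.1.

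**Second look, all enrolled.** The log-rank test can also use children not yet at one year. At the planned 54 per year, 92 + 54 = 146 would be enrolled, 73 per arm. If nearly all deaths are early, 23 v 41 crosses (z = 3.00 by two proportions, 3.04 by log-rank): 41/23 = 1.8.

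**Other placebo rates** (completers, continuous scale): 20% gives a ratio of 2.5, 25% gives 2.2, 35% gives 1.9 and 40% gives 1.8.

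**First look (already past).** With all 79 enrolled, about 39 per arm, 12 v 32 deaths crosses (z = 4.57; ratio 2.7).

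**Chance of crossing the lower limit by the second look, placebo 31%:**

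| True NAC mortality | Two proportions, completers | Log-rank, 125 to 146 enrolled, early deaths (mean 30 days) | For comparison: z ≤ −1.96 at second look, completers |
|---|---|---|---|
| 31% | 0.1% | – | 2.5% |
| 46.5% (1.5 × 31%) | 7.6% | about 11 to 13% | 32% |
| 50% | 13.4% | about 20 to 24% | 45% |

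The last column should be compared with the first results column, which uses the same test.

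**Effect of an illustrative −1.96 guideline on the error rates.** Under no effect, with correlation √(t₁/t₂) between looks, the chance of Z₁ ≤ −4.550, Z₂ ≤ −1.96 or Z₃ ≤ −1.969 is 0.041; with the printed limits it is 0.025. The upper tail stays at 0.025.

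**How many children remain.** At 54 per year, 184 − 146 = 38 would not yet be randomized at the second look. The first-look figures suggest slower accrual: 79 − 42 = 37 children over about 12 to 14 months, or 32 to 37 per year. That gives 124 to 129 enrolled and 55 to 60 remaining.

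**The case against.** The best defence is that stopping for harm is not tied to these limits. Section 4.5 lets the DSMB recommend termination on whatever it sees, and nothing says that a limit must be crossed first. A mortality guideline of the kind proposed commonly sits in a charter or monitoring plan; both exist, and either may already hold one. Symmetric limits also match the stated two-sided test. All of this stands, and it rules out several stronger readings:

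- A reader might infer that excess deaths would go unmonitored, or that randomization would have to run to 184 while the limit is uncrossed. The protocol says neither. The assurance that review "assures the investigators and the NIDDK that the trial can continue without jeopardizing patient safety" attaches to the committee's ongoing review of the data, not to the limits.
- A reader might infer that the first-look limit could not be reached. Among the 42 one-year children alone (6 placebo deaths of 21) it would take 21 of 21 NAC deaths (z = 4.83; 20 of 21 gives 4.45). With all 79 enrolled it is very strict but attainable.
- The words about efficacy describe the preceding single-look plan. They can equally be read as leaving safety to the DSMB's general review, so they do not show that the lower limit was meant as the harm rule.

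The defence does not remove the printed lower limits. They are the only numerical standard in the document, and the protocol does not say whether they apply to harm.

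**Conclusion.** The point holds as a design weakness, not as an arithmetic error or a gap in oversight. The printed limit for excess deaths is as strict as the limit for benefit. At the second look it would be crossed only at about 1.8 to 2.1 times the placebo deaths, and it would miss a one-half increase in mortality about nine times in ten.

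This rests on 31% placebo mortality and equal arms. The lower end of the ratio also assumes about 146 enrolled and mostly early deaths. It is a cheap improvement worth making, and its weight falls if the charter or monitoring plan already contains a mortality guideline.

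**What to change.** In 3.3.1 and 3.3.6, keep the upper (benefit) limits unchanged. Add that from the second look on the lower limits do not govern stopping for harm. Add a separate, non-binding guideline on all-cause death, less strict than −2.963, with the value set by the DSMB; z ≤ −1.96 is an example, crossed at 24 v 14 deaths among completers (z = 2.12; 23 v 14 gives 1.91). If the charter or monitoring plan already holds such a guideline, a cross-reference reconciling it with the printed lower limits is enough.

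The cost is about two sentences. With −1.96 there is about a 2.5% chance at the second look that a neutral drug prompts a harm discussion. The lower-tail error becomes about 0.041 instead of 0.025 if the guideline is always acted on, and there is a slight loss of power if the DSMB then stops. The type I error for benefit does not rise. The gain is limited: the first look is past, and about 124 to 146 of 184 children would already be randomized at the second, so roughly 38 to 60 could be affected.

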3.3.7 Efforts to Ensure Compliance with Protocol

Every effort will be made by study personnel to ensure protocol compliance. This includes enrollment of all eligible patients, providing data in a timely fashion, prompt notification of the pharmacist to obtain the treatment allocation, and proper administration of study treatment.

Site visits serve as important quality control checks and provide a means to become familiar with personnel and basic practices and procedures at each center. Clinical centers will have at least one site visit over the course of the study. The CCC PI and DCC personnel will visit each center and review source documents for a sample of patients, including patients with an exceptional number of inconsistencies identified through the data monitoring processes. At each site visit, the quality of data collection procedures will be assessed, the responsibilities of study personnel will be reviewed and visitors will confirm that data are collected in a timely and accurate manner. Problems with adhering to study protocols, data collection, and management within or between centers and within or between data collection personnel will be identified and addressed. In addition, site visitors will review subject recruitment and retention procedures, and other study specific administrative and organizational procedures. Site visits provide a means for the DCC to become familiar with personnel and basic practices and procedures at each center.

4.0 Human Subjects

4.1 General Characteristics – Minority Inclusion and Non-Discriminatory Statements

In general, ALF patients comprise somewhat more females than males, but there is no preponderance of any racial group, other than that expected on the basis of geographic differences. No exclusion will be made on the basis of race, ethnic group or gender. Criteria for inclusion of females and minorities will be those established in the NIH guidelines.

4.2 Inclusion of Children in Research

This research is restricted to children.

Intravenous NAC is a very safe agent with no significant side effects found during extensive use in Europe as well as sporadic use in the U.S. Individual children may or may not benefit from participation in this research.

In the future, other young people with acute liver failure could benefit from the results of this research. Information gained from this research could lead to improved medical care for them. However, your child's study doctor will not know whether there are benefits to other young people with acute liver failure until all of the information obtained from this research has been collected and analyzed.

4.3 Inclusion/Exclusion Criteria – Pregnancy and Birth Control Statements

INCLUSION CRITERIA

1. Enrollment in PALF registry (use PT INR results from the most recent tests performed prior to plasma therapy, but no more than 72 hours prior to enrollment in the registry.)
2. Informed consent obtained from the patient (when patient is 14-17 years of age or <17 and developmentally able to sign his or her name and is without clinical encephalopathy), parent, or guardian

EXCLUSION CRITERIA

1. Acute Acetaminophen toxicity
2. Patient on N-acetylcysteine or received N-acetylcysteine during the course of this illness.
3. Pregnancy
4. Known malignancy
5. Patient is on a liver support device
6. Sepsis
7. Signs of cerebral herniation
8. Intractable hypotension defined as systolic BP < 85 mm Hg or hypotension that requires treatment with inotropic drugs, other than renal dosing dopamine

All female subjects of childbearing potential will receive a pregnancy test prior to enrollment. Pregnant females are not eligible for participation in the NAC trial.

